8.5.2. Time-to-Event Endpoints

For a subject who is not known to have relapsed or died by the end of the study follow-up or data cutoff, RFS is censored on the date of the last available assessment of the subject.

For subjects with none of the events defined in EFS before the end of the study follow-up or data cutoff, EFS is censored at the date of the last available assessment of the subject.

For a subject who is not known to have died by the end of study follow-up or data cutoff, OS is censored on the date the subject was last known to be alive.

RFS, EFS and OS will be analyzed using Kaplan-Meier (KM) methods. The KM estimate of the survival function will be computed and the results will be presented using KM curves. The median will be provided along with the corresponding 95% CI. Additionally, the 25% and 75% percentiles for these endpoints will also be provided.

For subjects who die without report of relapse, remission duration is censored on the date of death, regardless of cause. For a subject with no report of relapse by the end of the study follow-up or data cutoff date, observation is censored on the date of the last available assessment of the subject.

Analysis of remission duration will be analyzed using cumulative incidence by considering competing risks. The estimate of the cumulative incidence of relapse (CIR) will be reported with the associated 95% CI.

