6.2.2. Analysis of the Secondary Endpoints

Subjects will be considered as treatment failure if having at least one efficacy assessment prior to SCT and other anticancer therapy (excluding SCT and conditioning regimen) but none of these efficacy assessments is CRc, CR, CRi, or PR; date of treatment failure will be the date of last adequate efficacy assessment prior to SCT and other anticancer therapy (excluding SCT and conditioning regimen). The events and censoring rules are detailed in [Table 6-1](#). Of note, other anti-cancer therapy excludes SCT and conditioning regimen in this table, and the criteria are hierarchical: subjects who meet the criteria on the top will be excluded from the criteria on the bottom.

Table 6-1. Event/Censoring Rules for EFS

Criteria	Event or Censored	Date of Event/Censoring
Relapse, no other anti-cancer therapy or prior to the start of other anti-cancer therapy, and 
 • had SCT prior to relapse, OR • no SCT prior to relapse, and days from last response assessment prior to relapse to relapse was within the following window (2 consecutive response assessments): For Group A: — ≤60 days (2 cycles (including the time waiting for	Event	Date of first relapse

count recovery) + 4 days) if didn't receive post-remission cycle
 
— <=120 days (4 cycles + 8 days) if received post-remission cycle but didn't receive ENTO mono maintenance cycle
 
— <=240 days (8 cycles + 16 days) if received ENTO mono maintenance cycle
		

For Group B:
 
— <=120 days (4 cycles + 8 days) if didn't receive maintenance cycle
 
— <= 240 days (8 cycles + 16 days) if received maintenance cycle
 
For Group C:
 
— <= 60 days (2 cycles + 4 days) if received <= 2 cycles
 
— <= 120 days (4cycles + 8 days) if received 3-4 cycles
 
— <= 240 days (8 cycles + 16 days) if received > 4 cycles
		

Treatment failure, and days from last response assessment prior to treatment failure or first dosing date, whichever is later, to treatment failure was within the window defined above
	
Event
	
Date of treatment failure

Death without treatment failure/relapse/other anti-cancer therapy, and
 
 • had SCT, OR • no SCT, and days from the date of last assessment or first dosing date, whichever is later, to the date of death was within the window defined above 	
Event
	
Date of death

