
No postbaseline assessment, no death
	
Censored
	
Date of first dose

No treatment failure/relapse/death
	
Censored
	
Date of last response assessment (and prior to other anti-cancer therapy if any) or first dosing date, whichever is later

Other anti-cancer therapy started prior to treatment failure/relapse/death	Censored	Date of last response assessment prior to other anti-cancer therapy or first dosing date, whichever is later
Days from last response assessment prior to treatment failure/relapse/death or first dosing date, whichever is later, to treatment failure/relapse/death was not within the window defined above	Censored	Date of last response assessment prior to treatment failure/relapse/death or first dosing date, whichever is later

Censoring Rules for OS:

- For a subject who is not known to have died by the end of study follow-up, OS is censored on the date the subject was last known to be alive.

For EFS or OS in months, the calculation is based on the following formula:

$$(\text{date of event/censoring} - \text{date of first dose} + 1) / 30.4375.$$

EFS and OS will be analyzed using Kaplan-Meier (KM) methods. The KM estimate of the survival function will be computed and the results will be presented using KM curves. The median will be provided along with the corresponding 95% CI. Additionally, the 25% and 75% percentiles for these endpoints will also be provided.

Follow up time for OS will be summarized as continuous variable with descriptive statistics.

- For a subject who is not known to have died by the end of study follow-up, duration of OS follow up in months = $(\text{date of last known to be alive} - \text{date of first dose} + 1) / 30.4375$
- For the remaining subjects, duration of OS follow up in months = $(\text{date of follow-up cutoff} - \text{date of first dose} + 1) / 30.4375$

Data listing for EFS and OS will be presented.

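### SAP Tables 6-1 and 6-2 censor and back-date observed relapses and deaths without SCT that fall outside an assessment-gap window; protocol 8.5.2 has no such window and SAP 6.5 does not list the change

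*SAP*

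**What the plan says.** **Protocol 8.5.2.** The EFS rule reads "For subjects with none of the events defined in EFS before the end of the study follow-up or data cutoff, EFS is censored", and the censoring date is given by "EFS is censored at the date of the last available assessment of the subject". The RFS rule is limited in the same way: "For a subject who is not known to have relapsed or died by the end of the study follow-up" or data cutoff. Neither contains a time window, a separate rule for SCT, or censoring at new therapy.

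**SAP 6.2.1.** EFS runs to treatment failure, relapse or death from any cause, with no time limit.

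**SAP 6.2.2, Table 6-1 (EFS).** A relapse with no prior SCT is an event only if "days from last response assessment prior to relapse to relapse was within the following window (2 consecutive response assessments") holds. A death with no SCT is an event only if the time from the last assessment, or from first dose if later, "to the date of death was within the window defined above". Treatment failure carries the same window. Relapses and deaths after SCT are exempt. The last row censors the remainder, where the interval from the last response assessment or the "first dosing date, whichever is later, to treatment failure/relapse/death was not within the window defined above". The censoring date is that last response assessment or first dose. Event-free subjects are censored at "Date of last response assessment (and prior to other anti-cancer therapy if any) or first dosing date, whichever is later". A further row censors at the start of other anti-cancer therapy.

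**SAP 6.3.2, Table 6-2 (RFS).** The rule is the same. For the cumulative incidence of relapse, only the in-window death row is coded as the competing event. All rows other than in-window relapse and in-window death are coded as censored.

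**SAP 6.5.** Only the time-to-blast-clearance (TTC) and MRD changes are listed.

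**The concern.** The tables discard events that are in the database. A death that counts in OS can be absent from EFS, although the SAP defines EFS by death from any cause. Whether a subject is censored at the earlier date depends on when the later event happens, so the censoring is informative. Subjects with and without SCT are scored by different rules.

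The outputs at stake are the EFS medians, quartiles and curves, the EFS curves by HOXA9/MEIS1 status (SAP 9), RFS, and the cumulative incidence of relapse. A reader of the CSR who relied on protocol 8.5.2 and SAP 6.5 would not know that any of this had been done.

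**Working it through.** **1. The windows reproduce.** With 28-day cycles: 2×28+4 = 60; 4×28+8 = 120; 8×28+16 = 240. Group B uses only 120 and 240.

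**2. Who is exposed.** Assessed non-responders are already treatment-failure events, and on schedule those failures fall inside the window. In Group B, first dose to Cycle 2 Day 28 is at most 14+56 = 70 days against 120. In Group C, first dose to Cycle 1 Day 28 is 28 days against 60. The rule therefore falls mainly on responders without SCT or new therapy, and on subjects who die with no assessment. The marrow that confirms a relapse does not help, because the gap is measured from the assessment before it.

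**3. Death with no assessment.** Take a Group A subject with no post-baseline assessment, post-remission cycle, SCT or other therapy who dies 70 days after first dose. Since 70 > 60, the death row fails. The rows for no death do not apply, so the last row censors the subject at first dose. Protocol 8.5.2 would count the death on its date.

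**4. Responder on treatment, Group A Phase 2, longest on-schedule path.** Inputs: 14-day lead-in and induction cycles of up to 28 days (protocol 6.3); post-remission marrows at Cycle 2 and Cycle 4 Day 28, and up to 12 maintenance cycles (protocol 3.1.2). Assumptions: each response assessment needs a marrow, and there are no unscheduled marrows.
- End of induction: 14+2×28 = Day 70.
- Post-remission marrows: 70+56 = Day 126 and 126+56 = Day 182.
- Maintenance: 12×28 = 336 days, Day 183 to Day 518.
- If the two post-remission marrows satisfy the waiver, the window ends at 182+240 = Day 422. An event on Days 423-518 (96 days) is censored at Day 182.
- If only maintenance marrows count, the second stable one is at 182+8×28 = Day 406. The window then runs to 406+240 = Day 646, beyond Day 518, and there is no on-treatment gap.

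Protocol 3.1.2 states the waiver under maintenance. Protocol Appendix 2 (Group A Phase 2, footnote q) and SAP 1.2 place it directly after both marrow schedules, which supports the first reading.

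**5. Responder after treatment.** Assume an end-of-treatment marrow on the last treatment day and follow-up to 3×365.25 ≈ Day 1096. Protocol 6.5 collects survival, leukemia treatments and other malignancies every 6 months, with no response assessment.
- After four post-remission cycles: events count to 182+120 = Day 302, which is 120 of the remaining 914 days (13%).
- After 12 maintenance cycles: events count to 518+240 = Day 758, which is 240 of 578 days (42%).

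The ±7-day visit window, and the allowance for a marrow up to 2 weeks earlier, shift these dates accordingly.

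**6. Cumulative incidence.** Protocol 8.5.2 says of remission duration both that deaths without relapse are censored at death and that competing risks are considered. SAP 6.3.2 moves an out-of-window death back to the last response assessment (or first dose, if later) as status 0, which matches neither statement.

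**7. Why the censoring date of event-free subjects matters.** Hypothetical case: ten responders last assessed on Day 70, of whom five die on Day 400 (330 days later, outside every window) and five are alive at Day 1096.
- Table 6-1: all ten censored at Day 70, no events, estimate 100%.
- Deaths counted, survivors censored at the last response assessment: 5 at risk, 5 deaths, estimate 0%.
- Deaths counted, survivors censored at last contact: 10 at risk, 5 deaths, estimate 50%.

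**The case against.** Censoring after missed assessments is a familiar convention, used because a relapse found after a long gap is poorly dated. The SAP ties its window to two consecutive assessments. That rationale carries some weight for relapse dates. It does not cover deaths, whose dates are known, or gaps that the protocol itself creates through the marrow waiver and the content of long-term follow-up.

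Several limits do stand:
- These are descriptive secondary and exploratory analyses, and by-subject listings are planned.
- The SAP introduction reports a lack of responses to monotherapy, early closure of Group B Phase 2 and early termination of the study. Exposed responders may be few, and actual follow-up shorter than Day 1096.
- The death row refers to the last assessment, not the last response assessment. A broad reading would rescue some deaths. Contacts about 183 days apart (155 to 211 with the 4-week allowance) still exceed the 60- and 120-day windows.
- The 6.3.2 narrative is redacted, so one cannot say that no unwindowed RFS or cumulative-incidence analysis is planned. For EFS, the readable text plans none.

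A reader might infer that counting every event and censoring survivors at last contact simply restores the protocol analysis. Protocol 8.5.2 does not say that. It uses the last available assessment for EFS and RFS and reserves the last-known-alive date for OS. Follow-up contacts do not record relapse status, so using them credits unassessed time as event-free.

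**Conclusion.** The departure is real and undisclosed. The SAP censors and back-dates observed relapses and deaths that protocol 8.5.2 and the SAP's own EFS definition count, and it treats subjects with SCT differently. SAP 6.5 omits the window, the SCT exemption and the new-therapy censoring. It should be fixed, but OS and the primary response rates are not affected.

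Two stronger readings are not supported. First, a reader might infer that the rule flatters EFS. The ten-subject example moves upward, but removing subjects from the risk set can also lower the estimate. In a simulation (40 subjects, exponential event times with a 12-month median, assessments every 28 days ending between Day 112 and Day 448, 240-day window), the mean one-year estimate was 0.37 windowed against 0.47 with events counted and survivors censored at last assessment. No direction should be asserted. Second, a reader might take Days 423-518 as a settled exposure of 96 of 336 maintenance days (29%). That holds only if post-remission marrows count toward the waiver; otherwise it is zero. The day ranges are illustrations of reach, not counts of affected subjects.

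**What to change.** 1. For EFS, RFS and the cumulative incidence of relapse, add an unwindowed analysis on existing data. Count every observed relapse, death and (for EFS) treatment failure on its own date, with or without SCT. Code every death without relapse as the competing event. Report it beside the windowed analysis.
2. State whether censoring at other anti-cancer therapy is kept; protocol 8.5.2 does not contain it.
3. State the censoring date for event-free subjects. Counting late deaths while censoring survivors at the last response assessment biases survival downward. Censor survivors at the last available assessment including follow-up contacts, and label this as an interpretation of 8.5.2. Note that those contacts do not record relapse, so event-free time may be overstated.
4. List the window, the SCT exemption and the new-therapy censoring in SAP 6.5, or in the CSR if the SAP is final.

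The cost is some wording and one extra run. Last-known-alive dates are already needed for OS ("OS is censored on the date the subject was last known to be alive"). The price in precision is that some relapses are dated less exactly, and an untreated relapse may be missed.

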6.3. Exploratory Efficacy Endpoints

6.3.1. Definition of the Exploratory Efficacy Endpoints

- **CCI** [REDACTED]
- [REDACTED]
- [REDACTED]
- [REDACTED]

- **CCI** [Redacted]
- [Redacted]

6.3.2. Analysis of the Exploratory Efficacy Endpoints

CCI [Redacted]

[Redacted]

[Redacted]

[Redacted]

Table 6-2. Event/Censoring Rules for RFS

Criteria	Event or Censored	Date of Event/Censoring

Relapse, no other anti-cancer therapy or prior to the start of other anti-cancer therapy, and
 
 • had SCT prior to relapse, OR • no SCT prior to relapse, and days from last response assessment prior to relapse to relapse was within the following window (2 consecutive response assessments): 
For Group A:
 
 — ≤ 60 days (2 cycles (including the time waiting for count recovery) + 4 days) if didn't receive post-remission cycle — ≤ 120 days (4 cycles + 8 days) if received post-remission cycle but didn't receive ENTO mono maintenance cycle — ≤ 240 days (8 cycles + 16 days) if received ENTO mono maintenance cycle 
For Group B:
 
 — ≤ 120 days (4 cycles + 8 days) if didn't receive maintenance cycle — ≤ 240 days (8 cycles + 16 days) if received maintenance cycle 
For Group C:
 
 — ≤ 60 days (2 cycles + 4 days) if received ≤ 2 cycles — ≤ 120 days (4cycles + 8 days) if received 3-4 cycles — ≤ 240 days (8 cycles + 16 days) if received > 4 cycles 	
Event
	
Date of first relapse

Death without relapse/other anti-cancer therapy, and 
 • had SCT, OR • no SCT, and days from the date of last assessment or first dosing date, whichever is later, to the date of death was within the window defined above 	Event	Date of death
No relapse/death	Censored	Date of last response assessment (and prior to other anti-cancer therapy if any) or first dosing date, whichever is later
Other anti-cancer therapy started prior to relapse/death	Censored	Date of last response assessment prior to other anti-cancer therapy or first dosing date, whichever is later
Days from last response assessment prior to relapse/death or first dosing date, whichever is later, to relapse/death was not within the window defined above	Censored	Date of last response assessment prior to relapse/death or first dosing date, whichever is later

Remission duration will be analyzed using cumulative incidence by considering competing risks. Relapse (the first situation in [Table 6-2](#)) is considered as the event of interest. Death without relapse (the second situation in [Table 6-2](#)) is a competing risk as death eliminates the occurrence of relapse. The other situations described in [Table 6-2](#) are considered as censored. There are three statuses: 0=censored, 1=relapse, and 2=death without relapse. SAS 9.4 PROC LIFETEST with statement TIME and option EVENTCODE=1 will be used. The estimates of the cumulative incidence of relapse (CIR) at 1, 3, 6, 12, 18, and 24 months (if appropriate) will be reported with the associated 95% CIs.

TTR will be summarized using descriptive statistics.

Data listing of TTR, RFS, and remission duration will be presented.

TTC will not be analyzed as data are not intensively measured/collected.

MRD rates will not be summarized as data are not measured/collected at all visits. A by-subject listing of MRD level will be provided.

The number and percentage of subjects who underwent SCT will be summarized and the corresponding 95% exact CI will be presented. In addition, the same analysis will be performed for subjects who underwent SCT at induction completion, post-remission, and maintenance completion, if applicable. A by-subject listing of SCT will be provided.

6.4. Other Efficacy Measures

Spaghetti plots of blasts (%) in bone marrow aspirate through the induction cycles for Group A and Group B and all cycles for Group C will be provided. For visits at which blasts in bone marrow aspirate are not available, blasts in bone marrow biopsy will be used. Since different subjects will be treated for different time periods per cycle and different number of cycles, the x-axis of the spaghetti plot, which is the study day, will be adjusted as follows to distinguish bone marrow results among the cycles:

Group A

For results in Cycle 1: Relative Day to Cycle 1 Day 1 + 15

For results in Cycle 2: Relative Day to Cycle 2 Day 1 + 102

Group B

For results in Cycle 1: Relative Day to Cycle 1 Day 1 + 16

For results in Cycle 2: Relative Day to Cycle 2 Day 1 + 61

For results in Cycle 3: Relative Day to Cycle 3 Day 1 + 106

For results in Cycle 4: Relative Day to Cycle 4 Day 1 + 151

A by-subject listing of bone marrow assessments, including both bone marrow aspirate and bone marrow biopsy, will be provided.

By-subject listings of ECOG performance status, cytogenetics, fluorescent in situ hybridization (FISH) analysis, and molecular mutation will be provided separately.

6.5. Changes From Protocol-Specified Efficacy Analyses

TTC will not be analyzed as data are not intensively measured/collected.

MRD rates will not be summarized as data are not measured/collected at all visits. A by-subject listing of MRD level will be provided.

7. SAFETY ANALYSES

Safety analysis will be presented by treatment group, phase, and dose level, treatment arm, or cohort if applicable, as elaborated in Section 3.2. Dose level for phase 1b is defined as the initial dose level a subject actually received.

7.1. Adverse Events and Deaths

7.1.1. Adverse Event Dictionary

Clinical and laboratory adverse events (AEs) will be coded using the current version of Medical Dictionary for Regulatory Activities (MedDRA). System organ class (SOC), high-level group term (HLGT), high-level term (HLT), preferred term (PT), and lower-level term (LLT) will be provided in the AE dataset.

7.1.2. Adverse Event Severity

Adverse events are graded by the investigator as Grade 1, 2, 3, 4, or 5 according to toxicity criteria specified in the Common Toxicity Criteria for Adverse Events (CTCAE) Version 4.03. The severity grade of events for which the investigator did not record severity will be categorized as “missing” for tabular summaries and data listings. The missing category will be listed last in data presentation.

7.1.3. Relationship of Adverse Events to Study Drug

Related AEs are those for which the investigator selected “Related” on the AE CRF to the question of “Related to Study Treatment GS-9973”, “Related to Study Treatment Cytarabine”, “Related to Study Treatment Daunorubicin”, “Related to Study Treatment Decitabine”, or “Related to Study Treatment Azacitidine”. Relatedness will always default to the investigator’s choice, not that of the medical monitor. Events for which the investigator did not record relationships to study drug will be considered related to study drug for summary purposes. However, by-subject data listings will show the relationship as missing.

7.1.4. Serious Adverse Events

Serious adverse events (SAEs) will be identified and captured as SAEs if AEs met the definitions of SAE specified in the study protocol. SAEs captured and stored in the clinical database will be reconciled with the SAE database from the Gilead Pharmacovigilance and Epidemiology before database finalization.

7.1.5. Treatment-Emergent Adverse Events

7.1.5.1. Definition of Treatment-Emergent Adverse Events

Treatment-emergent adverse events (TEAEs) are defined as 1 or both of the following:

- Any AEs with an onset date on or after the study drug start date and no later than 30 days after permanent discontinuation of study drug
- Any AEs leading to premature discontinuation of study drug

7.1.5.2. Incomplete Dates

AEs with incomplete onset dates will be identified and the incomplete dates will be imputed for TEAE determination. The imputation rules are as follows:

- If the day is missing but the month and year are available, then the imputed day will be the first day of the month or the first dosing date if they have the same month and year, whichever is later.
- If the day and month are missing but year is available, then the imputed day and month will be 01Jan or the first dosing date if they have the same year, whichever is later.

An AE with completely missing onset and stop dates, or with the onset date missing and a stop date later than the first dosing date of study drug, will be considered to be treatment emergent. In addition, an AE with the onset date missing and incomplete stop date with the same or later month and year (or year alone if month is not recorded) as the first dosing date of study drug will be considered treatment emergent.

